6.5.8 Hospitalization lasting >24 Hours

If the subject remains in the hospital >24 hours, perform the following daily until discharge:

1. Obtain routine clinical tests and evaluations in accordance with institutional guidelines and standard of care (e.g., vital signs, blood samples for standard clinical laboratory evaluations, ECG, etc.).
2. Assess and record adverse events, including bleeding and clinical efficacy endpoint events (MACE, stent thrombosis).
3. Review and record all concomitant medications taken during hospitalization.

If the subject remains in the hospital for \geq 48 hours, collect blood samples for optional research according to site participation and subject's individual consent (see **Section 6.6.3.2**) just prior to discharge:

- a. Samples for pharmacokinetics (plasma) and pharmacodynamics- platelet aggregation (whole blood) (PK/PD sub-study; participating sites only); and
- b. Plasma sample for exploratory biochemical, inflammatory and metabolic markers.

6.5.9 14 days (\pm 5 d) Post Study Drug Infusion Follow-Up Outpatient Visit

The subject will return to the investigational site approximately 14 days following their dosing with the study drug.

1. Review and record interval history since discharge including any concomitant illnesses, procedures, therapies (e.g., transfusions), adverse events, including bleeding and clinical

- efficacy endpoint events (MACE, stent thrombosis). The subject should be questioned regarding any hospitalization and/or medical visits relating to episodes of ischemia or bleeding or adverse events that may have occurred since discharge. Original source documents must be collected for any events. Should a subject be re-admitted or undergo care at an outside facility, all possible efforts should be made to obtain the original source documents.
2. Review and record concomitant medications (including maintenance anti-platelet treatment) taken since discharge.
 3. Perform a complete physical examination.
 4. Obtain vital signs, including heart rate and blood pressure.
 5. Record a standard 12-lead ECG.
 6. Obtain blood sample from the subject for the following standard clinical laboratory evaluations:
 - a. Hematology- complete blood count (CBC), differential white blood count and platelet count.
 7. Perform and document urine pregnancy test (urine beta-HCG point-of-care test) for all female subjects of child-bearing potential.
 8. Additional clinical laboratory tests and/or other evaluations may be performed for standard of care.
 9. Collect blood samples for optional research according to site participation and subject's individual consent (see **Section 6.6.3.2**):
 - a. Samples for pharmacokinetics (plasma) and pharmacodynamics- platelet aggregation (whole blood) (PK/PD sub-study; participating sites only); and
 - b. Plasma sample for exploratory biochemical, inflammatory and metabolic markers.
 10. Schedule follow-up telephone contact 30 days (\pm 5 d) post study drug administration.

6.5.10 30 days (\pm 5 d) Post Study Drug Infusion Follow-Up Telephone Contact

The subject will be contacted approximately 30 days following dosing with the study drug.

1. Review and record interval history since the 14-day study visit including any concomitant illnesses, procedures, therapies (e.g., transfusions), adverse events, including bleeding and clinical efficacy endpoint events (MACE, stent thrombosis). The subject should be questioned regarding any hospitalization and/or medical visits relating to episodes of ischemia or bleeding or adverse events that may have occurred since discharge. Original source documents must be collected for any events. Should a subject be re-admitted or undergo care at an outside facility, all possible efforts should be made to obtain original source documents.
2. Review and record concomitant medications (including maintenance anti-platelet treatment) taken since 14-day study visit.

3. Schedule follow-up phone contact for 90 days (\pm 7 d) post study drug administration.

6.5.11 90 days (\pm 7 d) Post Study Drug Infusion Follow-up Telephone Contact

The subject should be contacted approximately 90 days following dosing with the study drug.

1. Review and record interval history since the 30-day study telephone call including any concomitant illnesses, procedures, therapies (e.g., transfusions), adverse events, including bleeding and clinical efficacy endpoint events (MACE, stent thrombosis). The subject should be questioned regarding any hospitalization and/or medical visits relating to episodes of ischemia or bleeding or adverse events that may have occurred since discharge. Original source documents must be collected for any events. Should a subject be re-admitted or undergo care at an outside facility, all possible efforts should be made to obtain original source documents. Note that non-serious adverse events (bleeding and non-bleeding) will not be collected in the eCRF beyond the 30-day contact. All serious adverse events and clinical efficacy endpoint events will be collected through the 90-day contact.
2. Review and record concomitant medications (including maintenance anti-platelet treatment) taken since 30-day study telephone call.

Appropriate treatment for each subject after completing the study shall be at the investigator's discretion.

6.5.12 Non-PCI Subjects: Catheterization to Study Completion

Non-PCI subjects will receive medical management or CABG. The following provisions apply to all subjects when it is determined that PCI will not commence:

- Subjects should receive all subsequent care according to local standards.
- All post cardiac catheterization protocol-specified tests, evaluations and collections should be performed as per **Section 1.2** and **Section 6.5** and **Section 6.6** as usual.

Additional information/documentation for **medical management**:

- During the subject's hospitalization, the investigator or qualified designee should be sure to record the methods of medical management in source documentation/medical records and in the eCRF.

Additional information/documentation for **CABG**:

Every effort must be taken to obtain and record in source documentation and in the eCRF the following information for subjects who undergo CABG:

- Postoperative bleeding volume, measured by
 - chest tube drainage for the first 24 hours after completion of the procedure, and
 - total chest tube drainage;

- type and number of units of transfused blood products within a 48 hour period;
- reoperation following closure of the sternotomy incision for the purpose of controlling bleeding;
- abnormalities in laboratory tests for cardiac enzymes and CBC; and
- ECG abnormalities.

6.6 Study Procedures

The Study Flow Chart in **Section 1.2** summarizes the study procedures to be performed at each protocol time point. Individual study procedures are described below. For details of the procedures for assessment and reporting of adverse events, see **Section 6.7.2.2** (Assessment and Reporting of Adverse Events).

In order to minimize variability of evaluations, it is recommended that the same individuals perform the same types of evaluations for all subjects at each clinical site.

If a subject's participation in the study is discontinued for any reason, every attempt should be made to obtain final information for each test and evaluation as shown in the Study Flow Chart in **Section 1.2** pending the subject's consent to undergo the study-directed procedures and permission to disclose the corresponding information/data.

6.6.1 Standard Procedures and Clinical Evaluations

- **Explain Study and Obtain Written Informed Consent for the Main Study: Screening**

The investigator or qualified designee will explain the study to the prospective subject, answer all of his/her question (verbally or in writing), and obtain written informed consent before performing any study-related procedure. The investigator or qualified designee will also review acceptable methods of contraception (birth control) while taking part in this study with both female subjects of child-bearing potential and male subjects. The execution of the informed consent will be documented in the subject's medical records and a copy(s) of the informed consent(s) will be given to the subject.

- **Explain Optional Sampling for Pharmacokinetics/Pharmacodynamics, Exploratory Biomarkers and Pharmacogenomics: Screening**

The investigator or qualified designee will explain the optional sampling to the prospective subject, answer all of his/her question (verbally or in writing), and obtain written informed consent before performing any procedure related to the optional sampling. Written informed consent for the optional sampling for PK/PD sub-study (select sites only), exploratory biomarkers and pharmacogenomics (DNA and RNA) (**See Sections 6.6.3.2, 6.7.3 and Appendix E**) research may be contained in the same instrument as written informed consent for the rest of the study, or may be separate documents, at the discretion of the local Institutional Review Board (IRB). Regardless, separate signatures of informed consent are required to collect the optional samples for

PK/PD, exploratory biomarkers and pharmacogenomics research. Subjects who decline to sign the consent for optional research may still continue in the study. The execution of the informed consent will be documented in the subject's medical records and a copy(s) of the informed consent(s) will be given to the subject.

- **Review Inclusion/Exclusion Criteria (Including Prior and Current Medications and Therapies): Screening**

The inclusion and exclusion criteria will be reviewed by the investigator or qualified designee to ensure that the subject qualifies for the study. All medications and therapies during the 30 days prior to enrollment/randomization will be recorded in the source documentation and transcribed to the eCRF.

- **Medical History: Screening**

A medical history will be obtained by the investigator or qualified designee. Subject history should include information on family history and personal history. Subject history should include information concerning family history of chest pain and/or heart attack, general cardiac history, alcohol intake, smoking, as well as other coronary risk factors such as diabetes, hypertension, dyslipidemia, and obesity. Particular attention and documentation should be given to the subject's cardiac history, the clinical evaluation leading to the cardiac catheterization procedure (i.e., CAD presentation, Canadian Cardiovascular Society Classification for angina, Thrombolysis in Myocardial Infarction Risk Score for UA/NSTEMI, and New York Heart Association Classification of Functional Status for heart failure), bleeding history and allergy history (drugs, IV contrast media, food, stings and atopic conditions and any required treatment/ medical intervention).

- **Physical Examination: Screening, 24-hour/Discharge*, 14-day Visit**

The investigator or qualified designee will perform an examination to include skin, head, neck, pulses, lungs, heart, abdomen, extremities, and gross neurologic system. Abnormal findings not present at screening or abnormal findings that were present at screening but have become worse in severity/grading over baseline will be considered adverse events and recorded as per the AE procedures in **Section 6.7.2.2**.

*Note, the clinical site's standard of care, cardiac catheterization nursing assessment may be performed to evaluate the subject's clinical status in lieu of a complete physical exam at the 24 hour/discharge time point. This exam should be completed by qualified nursing staff with particular attention being paid to signs/symptoms related to the known side effects of PZ-128 (i.e., allergic reaction, injection site reaction and paresthesia) and other possible side effects from the procedure and/or concomitant medications (i.e., bleeding).

- **Vital Signs Assessment: Screening, Just Before Study Drug Infusion, Just After Completion of Study Drug, After Catheterization/PCI, 24-hour/Discharge, 14-day Visit**

At screening, the investigator or qualified designee will measure blood pressure and

pulse (after the subject has been supine for at least 5 minutes), and measure body weight and height without shoes and heavy clothing. Thereafter, only blood pressure and pulse will be measured. Measurements will be made with the subject lying down just before study drug infusion, just after study drug completion, after catheterization/PCI and 24-hour/discharge. Measurements will be made with the subject seated at the 14-day visit.

- **Assay- Pregnancy Test (Urine beta-HCG) for All Female Subjects of Child-Bearing Potential: Screening (must be within 24 hour of study drug administration), 14-day Visit**

The investigator or qualified designee will record the point-of-care urine beta-HCG test. If more frequent pregnancy testing is required by local standards of care, perform the testing as required and report pregnancy as specified in **Section 6.7.2.2.7**.

- **Electrocardiogram: Screening, After Catheterization/PCI, 14-day Visit**

A standard 12-lead ECG will be recorded by a qualified ECG technician or other qualified individual after the subject has been supine for at least 5 minutes. All ECG reports in the study must include heart rate (HR) and QRS, QT, QT_c (with method of correction) and PR intervals. Timing after catheterization/PCI will be dictated by standard practice and clinical signs/symptoms of cardiac ischemia.

- **Record Previous and Concomitant Medications and Therapies: Screening, 24-hour/Discharge, 14-day Visit, 30-day Phone Call, 90-day Phone Call**

Concomitant medications will be recorded in the subject's source documents and the appropriate section of the eCRF (See **Section 6.4.3**, Other Required Treatments and **Section 6.4.8**, Non-Study Treatments).

The following medications/therapies are exempt from being reported to the sponsor, unless they are deemed the cause of or contributor to an adverse event or used in the treatment of an adverse event:

- Electrolyte or nutritional replacement
 - IV fluids
 - Contrast media
 - Anesthetic medications that are inhaled or topical
 - Medications for surgical or nonsurgical procedures (e.g., sedatives, anesthetic)
 - Mediations/therapies that are not directly administered to the subject, such as cardioplegic solution or antithrombin used in conjunction with the cardiopulmonary bypass pump
 - Nonsystemic bowel prep (e.g., enema)
 - Vaccines
- **Adverse Events Assessment (Bleeding and Non-Bleeding): Continually During Hospitalization Following Enrollment/Randomization, 14-day Visit, 30-day Phone Call**

- **Serious Adverse Events Assessment (Bleeding and Non-Bleeding): Continually During Hospitalization Following Enrollment/Randomization, 14-day Visit, 30-day Phone Call, 90-day Phone Call**
- **Suspected Clinical Efficacy Endpoint Events (MACE & Stent Thrombosis): Continually During Hospitalization Following Enrollment/Randomization, 14-day Visit, 30-day Phone Call, 90-day Phone Call**

All adverse events (AEs) (bleeding and non-bleeding) will be reported to the sponsor in the eCRF from the time of randomization through 30 days after study drug administration. Only AEs which are classified as serious adverse events (SAEs) (bleeding and non-bleeding) will be reported to the sponsor in the eCRF after 30 days up until 90 days after study drug administration. All clinical efficacy endpoint events (MACE, stent thrombosis) will be reported to the sponsor from the time of randomization through 90 days after study drug administration.

Recording of adverse events, including reports by subjects, observations by study staff, and results of laboratory tests or other procedures, is described in **Section 6.7.2.2** (Assessment and Reporting of Adverse Events). Endpoint events (and associated symptoms) are identified as part of **Section 6.7.1** (Safety/Activity/Efficacy Endpoints) and are defined specifically in **Appendix B**, and will be detailed in the separate CEC charter for purposes of adjudication.

Note that clinical efficacy endpoint events- major adverse cardiac events (**MACE**) (any of cardiovascular death, non-fatal myocardial infarction (MI), non-fatal stroke, recurrent ischemia requiring hospitalization or urgent coronary revascularization) and **definite or probable stent thrombosis**- as well as **bleeding events** (safety) are considered “Clinical Endpoint Events” and will be adjudicated periodically during the conduct of the trial. The clinical endpoint events will be monitored in aggregate by the DSMB at appropriate intervals (i.e., quarterly). As such, these clinical endpoint events will not be reported separately in an expedited manner as “serious adverse events” to the sponsor’s SAE contact (see **Section 6.7.2.2.10**- Protocol-Specific Exceptions to SAE Reporting).

6.6.2 Standard Laboratory Tests

The investigator or qualified designee will collect all appropriate samples for analysis which will be then be performed at the local clinical laboratory on site. The values from Screening (Enrollment/Randomization) will be considered Baseline values for all standard laboratory tests. Results of testing should be reviewed by the investigator/qualified designee in a timely manner for pertinent clinically significant values. If any abnormal test result is considered to be clinically significant, the test should be repeated at appropriate time intervals until it returns to Baseline or becomes a clinically insignificant finding or the investigator/qualified designee decides it is not appropriate to continue.

- **Hematology: Screening, After Catheterization/PCI, 24-hour/Discharge, 14-day Visit**
Blood samples will be collected to quantify red blood cell (RBC) count, total and differential white blood cell (WBC) count, hemoglobin concentration, hematocrit, and platelet count. Timing after catheterization/PCI will be dictated by standard of care.
- **Serum Chemistry: Screening, 24-hour/Discharge**
Blood samples will be collected to quantify the following variables:
Sodium, potassium, chloride, carbon dioxide, glucose, blood urea nitrogen (BUN), creatinine, alkaline phosphatase, total bilirubin, alanine aminotransferase (ALT) and aspartate aminotransferase (AST).
- **PT/INR and aPTT: Screening, 24-hour/Discharge**
- **Activated Clotting Time: During and After PCI**
Following administration of the initial bolus of anti-coagulant, point-of-care testing of the activated clotting time (ACT) should be measured at “peak dose” and just prior to sheath removal, as well as according to the standard of care and local routine practice.
- **Lipid Panel: Screening**
Blood samples (does not need to be fasting) will be collected to quantify total cholesterol, high-density-lipoprotein cholesterol (HDL-C), calculated low-density-lipoprotein cholesterol (LDL-C) and triglycerides.
- **Glycosylated Hemoglobin: Screening**
Blood sample (does not require fasting) will be collected to quantify glycosylated hemoglobin (HgA1c) levels.

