- Written informed consent for the optional sampling: pharmacogenomics (DNA/RNA), pharmacodynamics-platelet aggregation, pharmacokinetics, and exploratory biomarkers may be contained in the same instrument as written informed consent for the rest of the study, or may be a separate document, at the discretion of the institutional review board (IRB). Regardless, separate signatures of informed consent are required to collect each of the optional samples.
- Including subject's cardiac history, the clinical evaluation leading to the cardiac catheterization procedure (i.e., CAD presentation, Canadian Cardiovascular Society Classification for angina, Thrombolysis in Myocardial Infarction Risk Score for UA/NSTEMI, and New York Heart Association Classification of Functional Status for heart failure), bleeding history and allergy history (drugs, IV contrast media, food, stings and atopic conditions and any required treatment/medical intervention).
- Vital signs to include heart rate, blood pressure, and at Screening only, height and weight.
- Hematology includes a complete blood cell count, differential WBC count and platelet count.
- Chemistry includes sodium, potassium, chloride, carbon dioxide, glucose, BUN, creatinine, alkaline phosphatase, total bilirubin, ALT and AST.
- Lipid Panel includes total cholesterol, high-density lipoprotein cholesterol, calculated low-density lipoprotein cholesterol and triglycerides (does not have to be fasting).
- Urine pregnancy test (urine beta-HCG) must be performed on all women of child-bearing potential prior to randomization and must also be repeated prior to study drug administration if screening assessment >24 hours.

8. Cardiac Troponin I (cTnI) analysis to be conducted by a centralized lab at Tufts Medical Center. Additional cardiac biomarkers (i.e., Troponin I or T, CK-MB) analyzed locally at the clinical site for routine management of the subject will be guided by standard of care/local hospital clinical practice and the results will be collected when applicable.
9. At select sites only in the Sub-study.
10. Screening evaluations must be performed prior to Enrollment/Randomization and must be within 14 days prior to cardiac catheterization and study drug treatment (may include standard of care preadmission testing for the planned procedure).
11. Study drug infusion must be started within 0-60 min prior to the commencement of the cardiac catheterization procedure (diagnostic angiography).

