6.5.1 Screening (within 14 days prior to cardiac catheterization/study drug administration)

Screening should occur as soon as a prospective study participant is identified. The investigator or qualified designee should ascertain as much as possible, and as allowed, that a subject would be eligible to participate before obtaining informed written consent. All screening parameters for enrollment must be performed prior to randomization and must be within 14 days before the cardiac catheterization/PCI and study drug administration. Subjects may or may not already be hospitalized due to their acute condition. Any data collected and any procedure performed as part of standard of care preadmission testing or other testing before written consent has been obtained may be used as part of the assessment for eligibility as long as it would have been performed regardless of subject participation in the study and it is within the specified time frame for inclusion/exclusion criteria (this includes data/results collected from another facility). All samples, tests, and evaluations collected/ performed/ recorded as part of the procedures specified in this protocol that are not part of standard of care may occur only after written informed consent has been obtained.

A subject who signs the informed consent to participate in the study but does not progress to a randomization assignment (by decision of either the subject or investigator) will be considered as a screen failure. Screen failure subjects will not be considered enrolled in the trial by the sponsor and will not be followed beyond the point it is determined that the subject will not be randomized- no further data will be collected, and the subject will not be included in any study safety and efficacy analyses. However, the investigator and/or designee will submit a log record of those subjects as per **Section 8.2**.

The clinical laboratory at each study site will be used to perform all standard clinical labs according to its internal SOP's unless otherwise stated.

The following will be performed or obtained during the baseline screening period prior to randomization:

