1. Explain the study to the subject and obtain appropriate written informed consents (i.e., main study and optional PK/PD sub-study, exploratory biomarkers research and pharmacogenomics). Review acceptable methods of contraception (birth control) while taking part in this study with both female subjects of child-bearing potential and male subjects.
2. Obtain a complete medical history (medical, surgical and cardiovascular) and demographics.
3. Review and record all previous and concomitant medications taken within the past 30 days with particular attention to anti-platelet, anticoagulant and thrombolytic/ fibrinolytic therapy.
4. Perform a complete physical exam (review of systems).
5. Obtain vital signs, including heart rate, blood pressure, and height and weight.
6. Record a standard 12-lead electrocardiogram (ECG).

7. Obtain blood samples from the subject for the following standard clinical laboratory evaluations to be performed locally:
 - a. Hematology- complete blood count (CBC), differential white blood count and platelet count;
 - b. Serum chemistry- sodium, potassium, chloride, carbon dioxide (CO₂), glucose, blood urea nitrogen (BUN), creatinine, alkaline phosphatase, total bilirubin, alanine transaminase (ALT), and aspartate transaminase (AST);
 - c. PT/INR and aPTT;
 - d. Lipid panel- total cholesterol, high-density lipoprotein cholesterol, calculated low-density lipoprotein cholesterol and triglycerides (does not have to be fasting); and
 - e. Glycosylated Hemoglobin (HbA1c).
8. Perform and document urine pregnancy test (urine beta-HCG point-of-care test) for all women of child-bearing potential (this must be completed during screening and also within the 24 hours prior to study drug administration). Perform eligibility assessment (review of inclusion & exclusion criteria, See **Section 6.3.1** and **Section 6.3.2**).

Subjects may be randomized prior to the return of the baseline local clinical laboratory test results unless the test is specifically listed in the inclusion/exclusion criteria (i.e., hemoglobin, hematocrit, platelet count). However, all baseline laboratory blood draws must be done prior to randomization and within the specified time frame (i.e., 14 days prior to study drug administration/cardiac catheterization ± PCI).

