6.5.3 Pre-Cardiac Catheterization Procedure

1. Prepare study drug for administration in investigational/research pharmacy (see *Investigational Product Instruction Manual-IPIM*).
2. Record any changes to concomitant medication(s).
3. Confirm subject still meets eligibility criteria to receive study drug.
4. Perform and document urine pregnancy test (urine beta-HCG point-of-care test) for women of child-bearing potential if screening assessment was not within the 24 hours prior to study drug administration. The result must be known and negative prior to administration of the study drug.
5. Administer aspirin.
6. 
7. Obtain vital signs, including heart rate and blood pressure just prior to study drug administration (i.e., Time=0).
8. Collect blood sample (serum) for centralized research analysis of Cardiac Troponin I (cTnI) just prior to study drug administration (i.e., Time=0).
9. Collect blood samples for optional research according to site participation and subject's individual consent (see **Section 6.6.3.2**) just prior to study drug administration (i.e., Time=0):
 - a. Samples for pharmacokinetics (plasma) and pharmacodynamics-platelet aggregation (whole blood) (PK/PD sub-study; participating sites only);
 - b. Plasma sample for exploratory biochemical, inflammatory and metabolic markers; and
 - c. Whole blood sample for pharmacogenomics.
10. **Start blinded PZ-128/placebo** IV administration 0-60 min prior to start of coronary angiography and infuse continuously over 2 hours (infuse entire contents for complete dosing). Observe anaphylaxis precautions during the infusion and for at least 1 hour following cessation of study drug.
11. Perform any additional standard of care assessments in the pre-cardiac catheterization/PCI setting.
12. Assess and record adverse events, including bleeding and clinical efficacy endpoint events (MACE, stent thrombosis).

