6.7.1 Safety/Activity/Efficacy Endpoints

6.7.1.1 Primary Endpoint (Safety)

The primary endpoint of the study will be the incidence of TIMI major plus minor bleeding not related to CABG through 30 days after treatment with the study drug. Definitions are as follows:

- TIMI Major bleeding is defined as
 - intracranial hemorrhage, or
 - clinically significant overt signs of bleeding associated with a decrease in hemoglobin concentration of ≥ 5 g/dL (or hematocrit $\geq 15\%$), or
 - fatal bleeding within 7 days.
- TIMI Minor bleeding is defined as clinically overt signs of bleeding (including imaging) associated with a decrease in hemoglobin concentration of 3 to < 5 g/dL (or hematocrit of 9 to $< 15\%$) that does not otherwise meet criteria for major bleeding.

Hemoglobin concentration and hematocrit will be adjusted for any transfusion of packed red blood cells or whole blood given between enrollment/randomization and the post-transfusion measurements by Landefeld and coworkers as follows:

$$\Delta \text{ Hemoglobin (Hgb)} = [\text{Baseline Hgb} - \text{post-transfusion Hgb}] + [\text{number of transfused units}]$$
$$\Delta \text{ Hematocrit (Hct)} = [\text{Baseline Hct} - \text{post-transfusion Hct}] + [\text{number of transfused units} \times 3]$$

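### The hemoglobin baseline that grades the primary TIMI endpoint is the Screening value, up to 14 days old, so change before the infusion misclassifies some bleeds in both directions and in both arms.

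*Combined protocol and SAP*

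**What the plan says.** Section 6.6.2 sets the baseline for every standard laboratory test, hematology included: "The values from Screening (Enrollment/Randomization) will be considered Baseline values for all standard laboratory tests". The flow chart (section 1.2, note 10) says that screening evaluations "must be within 14 days prior to cardiac catheterization and study drug treatment". Section 6.5.1 adds that "all baseline laboratory blood draws must be done prior to randomization and within the specified time frame", and it accepts routine results obtained before consent ("this includes data/results collected from another facility").

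The hematology schedule in 6.6.2 reads "Hematology: Screening, After Catheterization/PCI, 24-hour/Discharge, 14-day Visit". The flow chart, section 6.5.3 and Table 1 agree with it: none has a blood count between Screening and the post-catheterization sample. Section 6.5.3 does require another blood draw at that moment: "Collect blood sample (serum) for centralized research analysis of Cardiac Troponin I (cTnI) just prior to study drug administration".

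Section 6.7.1.1 grades bleeding by the hemoglobin fall. TIMI major includes "clinically significant overt signs of bleeding associated with a decrease in hemoglobin concentration of" 5 g/dL or more. TIMI minor is "clinically overt signs of bleeding (including imaging) associated with a decrease in hemoglobin concentration" of 3 to under 5 g/dL. Smaller falls are minimal bleeding (6.7.1.3), which is not a primary event. The transfusion correction in 6.7.1.1 and Appendix B subtracts the later value from the baseline value, and Appendix B equates baseline with enrollment.

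**The concern.** The primary endpoint is bleeding through 30 days after treatment, yet the reference value for its grading can predate treatment by two weeks. An elective outpatient may have been screened on day -12. An urgent inpatient may have a count on admission and later routine counts before catheterization. In both, hemoglobin may have moved before the infusion through fluids, phlebotomy or ordinary variation, and that movement is added to, or subtracted from, the fall credited to a later bleed.

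The boundary that matters most is 3 g/dL, because crossing it turns a minimal bleed into a primary event. Crossing 5 g/dL only moves an event from minor to major, and the primary endpoint pools the two. Few events are expected: section 7.7 assumes 2% to 6% on placebo, which is 4 to 12 events among 200 subjects. A few reclassified subjects are then a visible share of the total.

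**Working it through.** **1. What is measured.** For a subject with overt bleeding after the infusion:

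measured fall = (Screening − pre-infusion) + (pre-infusion − lowest value after infusion).

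Only the second term belongs to the period after treatment. The error runs both ways:
- A loss of 1.0 g/dL before infusion and 2.0 after reads 1.0 + 2.0 = 3.0: minimal is counted as minor.
- A rise of 1.0 before infusion and a fall of 3.5 after reads 3.5 − 1.0 = 2.5: a true minor bleed is missed.

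**2. Near the threshold.** The documents give no drift data. Assume a Screening-to-infusion change that is normal with mean 0 and SD s. Then P(measured fall ≥ 3 | true fall t) = 1 − Φ((3 − t)/s).
- s = 0.3, t = 2.5: 1 − Φ(1.67) = 4.8%.
- s = 0.8, t = 2.5: 1 − Φ(0.625) = 26.6%.

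By symmetry, the same shares of subjects with t = 3.5 are missed.

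**3. Over all overt bleeders.** Assume in addition that the true post-infusion fall is gamma with mean 1.5 and SD 1.1 g/dL, so that 9.7% truly reach 3 g/dL.

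| Drift SD (mean 0) | Share measured ≥ 3 | Measured / true | False among counted | Missed among true |
|---|---|---|---|---|
| 0.3 | 10.1% | 1.04 | 14% | 10% |
| 0.5 | 10.9% | 1.12 | 25% | 15% |
| 0.8 | 12.9% | 1.33 | 41% | 21% |

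The columns tie together as ratio × (1 − false) = 1 − missed; for example 1.33 × 0.59 = 0.79. The ratio exceeds 1 at zero mean drift only because more subjects lie just below 3 g/dL than just above it. A mean pre-infusion rise of 0.3 (SD 0.5) gives a ratio of 0.83, and a mean fall of 0.3 gives 1.51. The table is an illustration and not a bound.

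**4. In events.** At 2% in both arms, 600 subjects give 12 true events. If all are defined by hemoglobin, false events number 12 × 1.04 × 0.14 ≈ 2 up to 12 × 1.33 × 0.41 ≈ 7. Missed events number 12 × 0.10 ≈ 1 up to 12 × 0.21 ≈ 3.

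**5. Effect on precision.** The plan's only computed figure for this endpoint is the margin table in 7.7. With 200 and 400 subjects, one-sided 5%, 80% power and no true difference, the usual formula is

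margin = (1.645 + 0.842) × √[p(1 − p)(1/200 + 1/400)].

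It gives 3.01 points at p = 2% and 5.11 at 6%, where the table prints 2.6 and 4.4. That mismatch is a separate matter, and only the change is used here. Multiplying p by 1.04 to 1.33 moves 3.01 to 3.07–3.47 points and 5.11 to 5.21–5.84.

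**6. Effect on the difference.** If false events are additive at a rate f of 0.5% to 2% of subjects in each arm, a true 2-point difference becomes 2 × (1 − f) = 1.99 to 1.96. If instead both arms' rates are multiplied by the same ratio, the relative risk is unchanged and the risk difference grows by that ratio.

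**The case against.** The best defense is that hemoglobin alone never makes an event. The hemoglobin criteria need overt bleeding associated with the drop, intracranial and fatal bleeding do not depend on hemoglobin, and only events adjudicated by the blinded Clinical Events Committee (CEC) are analyzed (section 7.5). Active bleeding in the 30 days before randomization is an exclusion (6.3.2), and eligibility is reconfirmed before infusion (6.5.3). Fourteen days is a maximum, and many urgent inpatients will have fresher values. The CEC also works with additional instructions and a charter outside this document.

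All of this stands and limits the size. It does not remove the point, because among overt bleeds the hemoglobin fall is what separates minimal from minor. The visible text gives the CEC no rule for substituting a later value, and for many outpatients there may be no later value.

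Three stronger readings are tempting, and the documents do not support them:
- **A pre-infusion fall counts as a bleed.** It does not, because overt bleeding is required as well.
- **The CEC must ignore a later chart value.** No passage says so. Section 6.6.2 is a general rule for laboratory tests, and the text is silent on this case.
- **The noise pulls the comparison towards no difference and so helps a non-inferiority claim.** The estimand in 7.5.4 is a risk difference. Under the two models in step 6 it shrinks by at most 2% or grows, and a wider interval makes non-inferiority harder to show.

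**Conclusion.** The point holds as a problem of measurement precision in the primary endpoint. It rests on a stated rule and a complete schedule, not on a missing detail. Hemoglobin change between Screening and infusion enters the TIMI grading, adds some primary events and hides others, and does so without regard to arm. It adds noise and can widen the interval for the risk difference. It is not a bias for or against PZ-128.

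The size cannot be found from the documents. On the assumed inputs above, with zero mean drift, counted crossings are 1.04 to 1.33 times the true number, with 14% to 41% of them false and 10% to 21% of true crossings missed. Those figures move with the assumed distribution of falls, and the direction of the net count depends on the sign of the mean drift, which is unknown. The change is worth making because it is cheap, not because the trial's conclusion is shown to be at risk.

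**What to change.** In 6.6.2, 6.7.1.1 and Appendix B, define baseline hemoglobin and hematocrit for bleeding classification as the last value before the start of infusion, including local routine-care values, and count transfused units from that draw. Keep the Screening value for eligibility.

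Add one 4.5 mL hematology tube to the mandatory Time=0 draw (flow chart, 6.5.3, Table 1) for subjects enrolled from now on. The synopsis puts the first enrollment at 27 May 2016, so some subjects may already have been treated without such a sample. For those with no later pre-infusion value, the Screening value is the fallback.

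The cost is one local blood count and 4.5 mL per subject, with no extra venipuncture. The main-study blood volume in section 6.6.3.2 and Table 1 rises from 54–64 mL to 58.5–68.5 mL. Baseline recency will differ between earlier and later enrollees, but randomization balances that across arms.
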